9.1.3. Informed Consent Process

- The Investigator or his/her representative will explain the nature of the study to the participant or his/her legally authorized representative and answer all questions regarding the study.
- Participants must be informed that their participation is voluntary. Participants
 or their legally authorized representative will be required to sign a statement of
 informed consent that meets the requirements of 21 CFR 50, local regulations,
 ICH guidelines, Health Insurance Portability and Accountability Act (HIPAA)
 requirements, where applicable, and the IRB/IEC or study center.
- The medical record must include a statement that written informed consent was obtained before the participant was enrolled in the study and the date on which the written consent was obtained. The authorized person obtaining the informed consent must also sign the ICF.
- Participants must be re-consented to the most current version of the ICF(s) during their participation in the study.
- Copies of the ICF(s) must be provided to the participant or the participant's legally authorized representative.
- Participants who are rescreened are required to sign a new ICF.

The ICFs may contain a separate section that addresses the use of remaining mandatory samples for optional research in accordance with SOP-GSKF-410. The Investigator or authorized designee will explain to each participant the objectives of the research. Participants will be told that they are free to refuse to participate and may withdraw their consent at any time and for any reason during the storage period. A separate signature will be required to document a participant's agreement to allow any remaining specimens to be used for research. Participants who decline to participate will not provide this separate signature.

9.1.4. Data Protection

- Participants will be assigned a unique identifier by the Sponsor. Any participant records or datasets that are transferred to the Sponsor will contain the identifier only; participant names or any information which would make the participant identifiable will not be transferred.
- The participant must be informed that his/her personal study-related data will be used by the Sponsor in accordance with local data protection laws. The level of disclosure must also be explained to the participant.
- The participant must be informed that his/her medical records may be examined by Clinical Quality Assurance auditors or other authorized personnel appointed by the Sponsor, by appropriate IRB/IEC members, and by inspectors from regulatory authorities.

9.1.5. Committees Structure

A Translational Research Committee (made up of both internal and external experts) has been formed around this protocol to meet quarterly to discuss protocol design, development, and status.

9.1.6. Dissemination of Clinical Study Data

- Where required by applicable regulatory requirements, an investigator signatory will be identified for the approval of the clinical study report. The Investigator will be provided reasonable access to statistical tables, figures, and relevant reports and will have the opportunity to review the complete study results at a GSK site or other mutually-agreeable location.
- GSK will also provide the Investigator with the standard report of the tumor biopsy results, and applicable clinical trials, from DNAseq and RNAseq analysis initially performed on tumor biopsy.
- GSK will also provide a subset of CLIA-validated results back to participants through Gather Share Know Participant Hub. List of results that will be shared can be found in SRM.
- The procedures and timing for public disclosure of the protocol and results summary and for development of a manuscript for publication for this study will be in accordance with GSK Policy.
- GSK intends to make anonymized participant-level data from this trial available
 to external researchers for scientific analyses or to conduct further research that
 can help advance medical science or improve patient care. This helps ensure the
 data provided by trial participants are used to maximum effect in the creation of
 knowledge and understanding.
- A manuscript will be progressed for publication in the scientific literature if the results provide important scientific or medical knowledge.

9.1.7. Data Quality Assurance

- All participant data relating to the study will be recorded on eCRF unless transmitted to the Sponsor (or designee) electronically (e.g., laboratory data). The Investigator is responsible for verifying that data entries are accurate and correct by physically or electronically signing the eCRF.
- The Investigator must maintain accurate documentation (source data) that supports the information entered in the eCRF.
- The Investigator must permit study-related monitoring, audits, IRB/IEC review, and regulatory agency inspections and provide direct access to source data documents.
- The Sponsor (or designee) is responsible for the data management of this study including quality checking of the data.

- The Sponsor assumes accountability for actions delegated to other individuals (e.g., Contract Research Organizations).
- Monitoring details describing strategy (e.g., risk-based initiatives in operations and quality such as Risk Management and Mitigation Strategies and Analytical Risk-Based Monitoring), methods, responsibilities and requirements, including handling of noncompliance issues and monitoring techniques (central, remote, or on-site monitoring) are provided in the Monitoring Plan.
- Study monitors will perform ongoing source data verification to confirm that data entered into the eCRF by authorized site personnel are accurate, complete, and verifiable from source documents; that the safety and rights of participants are being protected; and that the study is being conducted in accordance with the currently approved protocol and any other study agreements, ICH GCP, and all applicable regulatory requirements.
- Records and documents, including signed ICF, pertaining to the conduct of this study must be retained by the Investigator for 25 years from the issue of the final Clinical Study Report (CSR)/ equivalent summary unless local regulations or institutional policies require a longer retention period. No records may be destroyed during the retention period without the written approval of the Sponsor. No records may be transferred to another location or party without written notification to the Sponsor.

9.1.8. Source Documents

- Source documents provide evidence for the existence of the participant and substantiate the integrity of the data collected. Source documents are filed at the investigator's site.
- Data reported/entered in the eCRF that are transcribed from source documents
 must be consistent with the source documents or the discrepancies must be
 explained. The Investigator may need to request previous medical records or
 transfer records, depending on the study. Also, current medical records must be
 available.

9.1.9. Study and Site Start and Closure

GSK or its designee reserves the right to close the study site or terminate the study at any time for any reason at the sole discretion of GSK. Study sites will be closed upon study completion. A study site is considered closed when all required documents and study supplies have been collected and a study-site closure visit has been performed.

The Investigator may initiate study-site closure at any time, provided there is reasonable cause and sufficient notice is given in advance of the intended termination.

Reasons for the early closure of a study site by the Sponsor or Investigator may include but are not limited to:

• Failure of the Investigator to comply with the protocol, the requirements of the IRB/IEC or local health authorities, the Sponsor's procedures, or GCP guidelines

- Inadequate recruitment of participants by the Investigator
- Discontinuation of further study intervention development

9.1.10. Publication Policy

- The results of this study may be published or presented at scientific meetings. If this is foreseen, the Investigator agrees to submit all manuscripts or abstracts to the Sponsor before submission. This allows the Sponsor to protect proprietary information and to provide comments.
- The Sponsor will comply with the requirements for publication of study results. In accordance with standard editorial and ethical practice, the Sponsor will generally support publication of multicenter studies only in their entirety and not as individual site data. In this case, a coordinating Investigator will be designated by mutual agreement.
- Authorship will be determined by mutual agreement and in line with International Committee of Medical Journal Editors authorship requirements.

9.2. Appendix 2: Clinical Laboratory Tests

- The tests detailed in Table 3 will be performed by the local laboratory.
- Protocol-specific requirements for inclusion or exclusion of participants are detailed in Section 5 of the protocol.
- Additional tests may be performed at any time during the study as determined necessary by the Investigator or required by local regulations.
- Pregnancy testing (urine or serum as required by local regulations) should be conducted as indicated in the SoA (Section 1.3).
- Pregnancy testing (urine or serum as required by local regulations) should be conducted throughout the time frame for female participant contraception in Section 5.1, Inclusion Criteria.
- Additional serum or urine pregnancy tests may be performed, as determined necessary by the Investigator or required by local regulation, to establish the absence of pregnancy at any time during the participant's participation in the study.

Table 3 Protocol-Required Safety Laboratory Assessments

Laboratory Assessments	Parameters		
Hematology	Platelet Count RBC Count Hemoglobin Hematocrit	RBC Indices: MCV MCH Reticulocytes	WBC count with Differential: Neutrophils Lymphocytes Monocytes Eosinophils Basophils
Coagulation	INR, PT, and aPTT		
Other Tests	 Highly sensitive serum or urine hCG pregnancy test (as needed for women of childbearing potential)^a HIV, HBV, HCV, HTLV, EBV, and syphilis (spirochete bacterium). 		

Abbreviations: aPTT = activated partial thromboplastin time; EBV = Epstein Barr virus; HBV = hepatitis B virus; HCV = hepatitis C virus; eCRF = electronic case report form; HIV = human immunodeficiency virus; HTLV = human T-lymphotropic virus; INR = international normalized ratio; MCH = mean corpuscular hemoglobin; MCV = mean corpuscular volume; PT = prothrombin time; RBC = red blood cells; WBC = white blood cells.

Note: All study-required laboratory assessments listed on Table 3 will be performed by a local laboratory; The results of each test must be entered into the eCRF.

a. Local urine testing will be standard for the protocol unless serum testing is required by local regulation or IRB/IEC.

9.3. Appendix 3: Adverse Events: Definitions and Procedures for Recording, Evaluating, Follow-up, and Reporting

9.3.1. Definition of AE

AE Definition

- An AE is any untoward medical occurrence in a clinical study participant, temporally associated with the use of a study intervention, whether or not considered related to the study intervention.
- NOTE: An AE can therefore be any unfavorable and unintended sign (including an abnormal laboratory finding), symptom, or disease (new or exacerbated) temporally associated with the use of a study intervention.

Events Meeting the AE Definition

- Any abnormal laboratory test results (hematology, clinical chemistry, or urinalysis) or other safety assessments (e.g., ECG, radiological scans, vital signs measurements), including those that worsen from baseline, considered clinically significant in the medical and scientific judgment of the investigator (i.e., not related to progression of underlying disease).
- Exacerbation of a chronic or intermittent pre-existing condition including either an increase in frequency and/or intensity of the condition.
- New conditions detected or diagnosed after study intervention administration even though it may have been present before the start of the study.
- Signs, symptoms, or the clinical sequelae of a suspected drug-drug interaction.
- Signs, symptoms, or the clinical sequelae of a suspected overdose of either study intervention or a concomitant medication. Overdose per se will not be reported as an AE/SAE unless it is an intentional overdose taken with possible suicidal/self-harming intent. Such overdoses should be reported regardless of sequelae.

Events NOT Meeting the AE Definition

- Any clinically significant abnormal laboratory findings or other abnormal safety assessments which are associated with the underlying disease, unless judged by the investigator to be more severe than expected for the participant's condition.
- The disease/disorder being studied or expected progression, signs, or symptoms of the disease/disorder being studied, unless more severe than expected for the participant's condition.
- Medical or surgical procedure (e.g., endoscopy, appendectomy): the condition that leads to the procedure is the AE.

- Situations in which an untoward medical occurrence did not occur (social and/or convenience admission to a hospital).
- Anticipated day-to-day fluctuations of pre-existing disease(s) or condition(s) present or detected at the start of the study that do not worsen.

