6. STUDY INTERVENTION

Study intervention is defined as any investigational intervention(s), marketed product(s), placebo, or medical device(s) intended to be administered to a study participant according to the study protocol.

No investigational therapeutic product will be used in Study 213299. MDCI is primarily an study that may inform subsequent clinical trial eligibility. Therapeutic interventions resulting from use of the investigational device results vary for each respective subsequent therapeutic clinical study protocol and will therefore be described under those specific protocols. Consequently, the following sections are not applicable to this protocol:

Study Intervention(s) Administered
Preparation/Handling/Storage/Accountability
Measures to Minimize Bias: Randomization and Blinding
Study Intervention Compliance
Concomitant Therapy
Dose Modification
Intervention after the End of the Study

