9.3.2. Definition of SAE

If an event is not an AE per definition above, then it cannot be an SAE even if serious conditions are met (e.g., hospitalization for signs/symptoms of the disease under study, death due to progression of disease).

An SAE is defined as any untoward medical occurrence that, at any dose, meets one or more of the criteria listed:

- o Results in death
- o Is life-threatening

The term 'life-threatening' in the definition of 'serious' refers to an event in which the participant was at risk of death at the time of the event. It does not refer to an event, which hypothetically might have caused death, if it were more severe.

Requires inpatient hospitalization or prolongation of existing hospitalization

- In general, hospitalization signifies that the participant has been detained (usually involving at least an overnight stay) at the hospital or emergency ward for observation and/or treatment that would not have been appropriate in the physician's office or outpatient setting. Complications that occur during hospitalization are AE. If a complication prolongs hospitalization or fulfills any other serious criteria, the event is serious. When in doubt as to whether "hospitalization" occurred or was necessary, the AE should be considered serious.
- Hospitalization for elective treatment of a pre-existing condition that did not worsen from baseline is not considered an AE.

Results in persistent or significant disability/incapacity

- The term disability means a substantial disruption of a person's ability to conduct normal life functions.
- This definition is not intended to include experiences of relatively minor medical significance such as uncomplicated headache, nausea, vomiting, diarrhea, influenza, and accidental trauma (e.g. sprained ankle) which may interfere with or prevent everyday life functions but do not constitute a substantial disruption.

Is a congenital anomaly/birth defect

Other situations:

- Medical or scientific judgment should be exercised in deciding whether SAE reporting is appropriate in other situations such as important medical events that may not be immediately life-threatening or result in death or hospitalization but may jeopardize the participant or may require medical or surgical intervention to prevent one of the other outcomes listed in the above definition. These events should usually be considered serious.

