9.3.3. Recording and Follow-Up of AE and SAE

AE and SAE Recording

- When an AE/SAE occurs, it is the responsibility of the investigator to review all documentation (e.g. hospital progress notes, laboratory, and diagnostics reports) related to the event.
- The investigator will then record all relevant AE/SAE information in the CRF.
- It is **not** acceptable for the investigator to send photocopies of the participant's medical records to GSK in lieu of completion of the GSK /AE/SAE CRF page.
- There may be instances when copies of medical records for certain cases are requested by GSK. In this case, all participant identifiers, with the exception of the participant number, will be redacted on the copies of the medical records before submission to GSK.
- The investigator will attempt to establish a diagnosis of the event based on signs, symptoms, and/or other clinical information. Whenever possible, the diagnosis (not the individual signs/symptoms) will be documented as the AE/SAE.

Assessment of Intensity

The investigator will make an assessment of intensity for each AE and SAE reported during the study and assign it to 1 of the following categories:

- Mild: An event that is easily tolerated by the participant, causing minimal discomfort and not interfering with everyday activities.
- Moderate: An event that causes sufficient discomfort and interferes with normal everyday activities.
- Severe: An event that prevents normal everyday activities. An AE that is assessed as severe should not be confused with an SAE. Severe is a category utilized for rating the intensity of an event; and both AE and SAE can be assessed as severe.

An event is defined as 'serious' when it meets at least 1 of the predefined outcomes as described in the definition of an SAE, NOT when it is rated as severe.

Other measures to evaluate AE and SAE may be utilized (e.g. National Cancer Institute Common Terminology Criteria for Adverse Events (NCI-CTCAE).

Assessment of Causality

- The investigator is obligated to assess the relationship between study intervention and each occurrence of each AE/SAE.
- A "reasonable possibility" of a relationship conveys that there are facts, evidence, and/or arguments to suggest a causal relationship, rather than a relationship cannot be ruled out.
- The investigator will use clinical judgment to determine the relationship.

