1.2. Study Design

Footnotes: ¹MDCI will be an optional protocol under select GSK oncology protocols; ²In the case that Visit 1 and 2 are combined, all corresponding samples must be collected per the SoA (Protocol Section 1.3) at this visit and after eligibility is confirmed; ³Subset of data to be shared on Gather Share Know; ⁴Patient's molecular profile and medical history will be compared against the eligibility criteria of select GSK oncology protocols to identify potential trial options; ⁵Visit 3 may occur remotely via

Overview of Study Design and Key Features		
Study	Not applicable	
intervention		
Study	Not applicable	
intervention		
Assignment		
Interim	Due to the continuous nature of this study, there is no interim analysis	
Analysis	phase.	

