4.5. Safety Analyses

The safety analyses will be based on the Enrolled Analysis Set, unless otherwise specified.

Only the AEs/SAEs related to study procedures are collected in this study. If there are no AEs/SAEs in the database, a standard 'No data to report' display will be generated.

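### Appendix 3 ties adverse events and causality to a study intervention that this study does not administer, while the Schedule of Activities, Section 7.5.1 and SAP 4.5 go by relation to study procedures

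*Protocol*

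**What the plan says.** Sections 7.5 and 7.5.2 of the protocol name Appendix 3 as the place for the AE and SAE definitions and for the method of assessing causality. Appendix 3 then says:

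- Section 9.3.1: "An AE is any untoward medical occurrence in a clinical study participant, temporally associated with the use of a study intervention".
- Section 9.3.2: "If an event is not an AE per definition above, then it cannot be an SAE even if serious conditions are met", and "An SAE is defined as any untoward medical occurrence that, at any dose, meets one or more of the criteria listed".
- Section 9.3.3: "The investigator is obligated to assess the relationship between study intervention and each occurrence of each AE/SAE". The timing to be weighed is that of study-intervention administration, and the Investigator's Brochure or product information is to be consulted.

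Section 6 defines study intervention as "any investigational intervention(s), marketed product(s), placebo, or medical device(s) intended to be administered to a study participant according to the study protocol". It continues: "No investigational therapeutic product will be used in Study 213299", and it lists the section on interventions administered among those that do not apply. SAP 1.2 enters "Not applicable" against study intervention. Neither document names biopsy, blood collection or imaging as the study intervention.

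Other places use a different exposure. Both Schedule of Activities tables call for review of AEs and SAEs that are related to study procedures or lead to study withdrawal. Section 2.3.1 asks sites to follow up AEs related to the study procedure. Section 4.1 speaks of SAEs related to protocol-mandated procedures or leading to withdrawal. Section 7.5.1 requires SAEs related to study participation (its examples include mandated procedures and invasive tests) or to a GSK product to be recorded from consent. SAP 4.5 states: "Only the AEs/SAEs related to study procedures are collected in this study".

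**The concern.** The definition decides what counts as an event, and the causality question decides what the event is attributed to. Both point to an exposure that the study does not give. The exposures it does give are procedures, and Section 2.3.1 calls specimen acquisition the primary risk to patients.

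Three things depend on this wording: whether a site classes a complication as an AE at all, whether the 24-hour SAE duty in Section 7.5.1 is triggered, and whether the event reaches the SAP 4.5 displays. SAP 4.5 provides a standard empty display if the database holds no AEs. If that display resulted from sites following Appendix 3 to the letter, it would look like a clean record for the biopsies.

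**Working it through.** The point turns on text, so the passages are set side by side first. The arithmetic only gives a scale.

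**1. Exposure named in each place**

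| Place | Function | Exposure |
|---|---|---|
| Protocol 9.3.1 | defines AE | study intervention |
| Protocol 9.3.2 | defines SAE | AE as above; dose wording |
| Protocol 9.3.3 | causality | study intervention and its administration |
| Schedule, Tables 1 and 2 | collection | study procedures, or leads to withdrawal |
| Protocol 2.3.1, 4.1 | follow-up | study procedures (4.1 also withdrawal) |
| Protocol 7.5.1 | SAE recording from consent | study participation, or a GSK product |
| SAP 4.5 | analysis | study procedures only |

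**2. One event followed through both sets of rules**

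Take bleeding after an outpatient Visit 2 biopsy that leads to admission.

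- Appendix 3, read literally: no study intervention was used, so the AE definition is not met. By 9.3.2 the event then cannot be an SAE. If it is entered anyway, relation to study intervention is no.
- Schedule and Section 7.5.1: the event is related to a mandated procedure, so it is collected, recorded and reported within 24 hours.

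The two routes give opposite answers for the same patient.

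**3. Does other text close the gap?**

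- The schedule row selects among AEs and SAEs. It does not say what an AE is, and Section 7.5 leaves that to Appendix 3.
- Section 9.3.1 also counts clinically significant abnormal safety findings, radiological scans included, and 9.3.2 counts complications arising during a hospital stay. These let some procedure events in. They do not plainly cover pain, bleeding or infection after an outpatient procedure, which are risks that Section 2.3.1 names.
- Section 7.5.1 has been adapted to this study: it separates medical history from AEs by the start of procedures. Section 9.3.1 still has an overdose bullet that mentions study intervention. The adaptation looks incomplete.

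**4. Scale**

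Inputs from Section 2.3.1: 26 patients with grade 3 and 7 with grade 4 biopsy events among 4,627, and an anticipated serious-complication rate below 2%. Section 8.2 gives 400 participants.

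- Reproducing the cited rates: 26/4,627 = 0.56% and 7/4,627 = 0.15%, which round to the stated 0.6% and 0.2%.
- Combined, assuming no patient is in both counts: p = 33/4,627 = 0.713%.
- The number n of fresh biopsies is not stated, so it is assumed. Archival or surplus tissue comes first (Section 5.1), so n can be as low as 0, and one fresh biopsy for each of 400 participants is taken as the upper end.
- Expected events = n × p; P(at least one) = 1 − (1 − p)^n; ceiling = 0.02 × n.

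| n (assumed) | Expected grade 3-4 | P(at least one) | 2% ceiling |
|---|---|---|---|
| 0 | 0 | 0% | 0 |
| 40 | 0.3 | 25% | 0.8 |
| 200 | 1.4 | 76% | 4 |
| 400 | 2.9 | 94% | 8 |

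**The case against.** The strongest reply is that the working parts of the protocol already cover procedure events. The schedule, Sections 2.3.1, 4.1 and 7.5.1 all call for them, and 7.5.1 sets the 24-hour rule. A site would have to ignore these to report nothing. That stands: the intent is clear, and many sites would probably report correctly.

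A reader might infer more: that procedure complications are not AEs in this study, that none would be captured, and that no causality field fits them. The documents do not support this.

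- Exclusion follows only from the most literal reading of one appendix, and other sections contradict that reading.
- The eCRF is not among the documents, so the content of its causality item is unknown. Table 1 of the schedule (footnote 13) and Section 7.5.1 both presuppose a judgement of relation to procedures or to study participation.
- Contrast is a weak example. Section 6 covers marketed products administered under the protocol, and Section 7.2.2 specifies contrast CT at Visit 2, so contrast can be read as a study intervention. Biopsy and blood draws cannot easily be read that way.
- The event counts show how many events the wording might touch. They do not show that any would be lost.

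What remains is that the text named as the source of the definitions and the causality method conflicts with the rules for collection and analysis.

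**Conclusion.** Wrong as written. Appendix 3 sets the AE definition, the bar on SAEs and the causality question by study intervention, while collection and analysis go by study procedure. Both cannot be followed literally for a biopsy or blood-draw complication.

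The finding is an unreconciled contradiction, with no demonstrated under-reporting. It rests on the text alone and does not depend on the assumed biopsy numbers. Those numbers show only that few serious events are likely, so the classification of a single case could decide whether the SAP 4.5 tables are empty.

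A related mismatch should be settled at the same time: SAP 4.5 mentions only procedure-related events, while the schedule also collects events leading to withdrawal.

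**What to change.** In the protocol:

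- State in 9.3.1 to 9.3.3 that, for this study, the AE and SAE definitions, the timing and the causality assessment refer to protocol-mandated procedures: tumor biopsy, blood collection, and study imaging including contrast. Alternatively, name these procedures as the study intervention in Section 6.
- Make the causality item record relation to study procedure. Keep a separate item for relation to a GSK product, because Section 7.5.1 needs it.
- Remove the dose phrase from the SAE definition, and the references to study-intervention administration or overdose that cannot apply. Keep the part of the overdose bullet that concerns concomitant medication.

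In the SAP, have 4.5 report events related to a study procedure and events leading to study withdrawal, in line with the schedule. Selecting on a procedure yes/no field alone would drop the withdrawal events.

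Check that the eCRF causality item matches. The cost is protocol and SAP wording plus that check. No visits or tests are added.
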